## **8. Study design/methodology:**

Randomized clinical trial with 39 adults with self-reported chronic neck pain recruited. They were randomly assigned into two groups. The experimental group received online exercise therapy and the control group received conventional exercise therapy.

Participants in both groups completed the same exercise program three times a week for six weeks with either face-to-face or online mode of delivery by physiotherapists. The degree of pain was assessed by the improvement in average and maximum visual analogue scale (VAS). Neck function and work limitations were assessed by the Neck Disability Index (NDI) and Work Limitations Questionnaire (WLQ) respectively. The Hospital Anxiety and Depression Scale (HADS) and its subscales were used to evaluate anxiety and depressive symptoms. Participants were assessed at baseline and at 6 weeks while the changes in WLQ were assessed biweekly. To ensure the effectiveness of online exercise therapy, therapists delivered the online exercise 3 times a week for 6 weeks, with videoconferencing once a week and posting of exercise record on WeChat app twice a week.

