## **10. Interventions:**

Participants in both groups completed the same exercise program three times a week for six weeks with either face-to-face or online mode of delivery by physiotherapists.

At baseline, the suitable elastic bands (Thera-band®) for performing the exercises were selected by testing the 15 repetitions maximum (15RM) of the Modified Brügger's Exercise (MBE) and the Modified Proprioceptive Neuromuscular Facilitation Diagonal Flexion Exercise (MPNFDDE) for the participants of both the experimental group and control group. The details of the MBE and MPNFDDE were described in supplementary file 1.

Participants randomized to the control group performed the following exercises three times a week for six weeks in a group of 3-5 participants in the laboratory of the Sport Medicine and Rehabilitation School of the Beijing Sport University:

- A. Warm-up exercises
- B. Cranio-cervical flexion exercises
- C. Strength-endurance exercises
- D. Scapular stabilization exercises
- E. Stretching exercises

[figure not shown]
The details of the exercises were described in supplementary file 2.

Participants allocated to the experimental group performed the same set of exercise three times a week for six weeks in their home, with the following arrangements:

The participants had weekly online exercise meetings with the physiotherapist in a group of 3-5 participants using the TENCENT Meeting. Then the participants performed the remaining two sessions of exercises themselves weekly. If they had encountered any problems, they could consult the physiotherapist during the online session or texting to the physiotherapist using the WeChat app. All the participants of the experimental group received a package of exercise pamphlet and a video disc containing 17-minute exercise demonstrations by the physiotherapist.

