## 11. Study Schedule:

CONSORT 2010 Flow Diagram

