## 12. Adverse Event Reporting:

In this study, the tests and interventions may include physical activities, which may irritate neck pain and have little risk of heart attack and other life-threatening conditions. During the test and trial, if there are adverse reactions such as acute aggravation of neck pain, the test or intervention will be stopped immediately, and emergency treatment will be conducted. If there is any emergency, the principal investigator(s) will provide basic life support including chest compressions and ventilation until emergency medical staff are on hand. Participant can consult the general practitioners if they

are experiencing any side effects from taking part in the study and should also inform the Principal Investigator.

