### **13. Statistical Analysis Plan:**

Continuous data were expressed as means and standard deviations. Categorical data were shown as frequencies or percentages. All statistical analyses were conducted using the IBM SPSS Statistics for Windows, Version 24.0 (Armonk, NY: IBM Corp). The normality of continuous data was checked with the Shapiro-Wilk test. The change scores of the primary and secondary outcome variables from baseline to end of intervention between the two groups were compared using independent sample t test. Within-group comparisons were done using paired sample t test. The level of significance of all statistical tests was set with two-tailed at 0.05. Per-protocol analysis was used. The sample size for the study was calculated to be 32 using the G\*Power 3.1.9.2 (Universitat Kiel, Germany), with an estimated effect size of group difference of 0.9 in primary outcomes and a level of significance of 0.05, statistical power of 80% with two-tailed independent sample t test. The estimated effect size was based on previous studies of home exercise on patients with neck pain (Zronek et al., 2016). With an anticipated dropout rate of 15%, a total of 39 participants was required.

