### **14. Informed Consent Process:**

Before participating in the study, physiotherapists will explain this study to all participants to ensure they are clear about this study. Participants can drop out at any time during this study. Then they will complete the informed consent form. All the participants are recruited from Beijing Sport University, China, and they are all native Chinese speakers, so the informed consent form is in Chinese (simplified). All participants should meet the inclusion criteria, and anyone meets the exclusion criteria will be excluded.

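### Per-protocol is the only analysis set named and the visible text does not define it, so exclusions could relate to arm and outcome; whether they did, and any bias, is unknown

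*Combined protocol and SAP*

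**What the plan says.** Section 13 compares change scores from baseline to end of intervention between the two groups with an independent-sample t test, two-tailed at 0.05. On who is analysed it says only "Per-protocol analysis was used". The visible text has no attendance threshold, no list of excluding deviations, no as-assigned analysis, no missing-data method and no non-inferiority margin.

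Other sections bear on who might be left out:

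- Section 10, control arm: sessions are held "three times a week for six weeks in a group of 3-5 participants in the laboratory".
- Section 10, online arm: one videoconference meeting a week, and "Then the participants performed the remaining two sessions of exercises themselves weekly". Section 8 describes the arrangement as "with videoconferencing once a week and posting of exercise record on WeChat app twice a week".
- Section 12: "if there are adverse reactions such as acute aggravation of neck pain, the test or intervention will be stopped immediately".
- Section 14: "Participants can drop out at any time during this study".
- Section 8, on outcome timing: "Participants were assessed at baseline and at 6 weeks while the changes in WLQ were assessed biweekly".

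Section 11 consists of a "CONSORT 2010 Flow Diagram" whose content is not shown. The two supplementary files are not shown either; Section 10 describes them as exercise details.

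**The concern.** Randomisation makes the two groups comparable as assigned. A per-protocol set gives up that protection unless exclusion is unrelated to outcome, or relates to it in a way that cancels between the arms. Here neither can be judged, because the rule is not stated. Per-protocol could mean removing non-adherent participants who do have week-6 data, or only those without week-6 data.

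Two features of this trial make the question more than formal. The evidence of adherence differs by arm: all control sessions take place in the laboratory, while two thirds of the online sessions are done alone and known through posted records. A single adherence rule could therefore act differently in the two arms, and delivery mode is what the trial compares. Also, the event that stops the intervention, acute aggravation of neck pain, is close to a primary outcome. If exclusions differ by arm and relate to improvement, the VAS and NDI comparisons can be biased toward either arm, and no other planned analysis would reveal it.

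**Working it through.** **Sessions (Sections 8 and 10).** Control: 3 × 6 = 18 in the laboratory. Online: 1 × 6 = 6 by videoconference and 2 × 6 = 12 self-performed.

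**What the plan quantifies.** It gives no figure for per-protocol exclusions. The nearest is the 15% dropout in Section 13: 0.15 × 39 = 5.85, about 6 people, leaving 33. This is borrowed only to set a scale; it is not an adherence-exclusion rate.

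**Assumptions, none from the documents.** Arms of 20 online and 19 control (the allocation ratio is not stated), 6 excluded in total, SD of change 1, no true difference as assigned, and those excluded improving k = 0.5 to 1.0 SD less than those retained.

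**Formula.** Let e be the share of an arm excluded. Full-arm mean = (1 − e) × retained mean + e × excluded mean, so retained mean − full-arm mean = e × k. Hence

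bias = e_online × k_online − e_control × k_control,

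with positive values favouring online. The false-positive rate is the two-tailed rejection probability of the two-sample t test at 0.05, from the noncentral t distribution with noncentrality bias / √(1/n₁ + 1/n₂).

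**Example, 6 online and 0 control excluded.** Bias = 6/20 × k = 0.15 (k = 0.5) or 0.30 (k = 1.0). With 14 and 19 analysed, SE = √(1/14 + 1/19) = 0.352, and rejection is 7.0% or 13.1%.

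**Same gap k in both arms:**

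| Excluded online / control | Analysed | Bias, SD (k = 0.5; 1.0) | False-positive rate |
|---|---|---|---|
| 6 / 0 | 14 / 19 | +0.15; +0.30 | 7.0%; 13.1% |
| 5 / 1 | 15 / 18 | +0.10; +0.20 | 5.9%; 8.5% |
| 4 / 2 | 16 / 17 | +0.05; +0.09 | 5.2%; 5.8% |
| 3 / 3 | 17 / 16 | about 0 | 5.0%; 5.0% |
| 1 / 5 | 19 / 14 | -0.11; -0.21 | 6.0%; 9.0% |
| 0 / 6 | 20 / 13 | -0.16; -0.32 | 7.1%; 13.8% |

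**Gap differing by arm.** Three excluded from each arm, with k = 1.0 online and 0 in control: bias = 3/20 × 1.0 − 3/19 × 0 = +0.15 SD, false-positive rate 7.0%. Equal counts are therefore no reassurance by themselves.

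**Reversal.** If those excluded improve more than those retained, every sign reverses.

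**Comparator.** In 200,000 simulated trials for the 5/1, 4/2, 3/3 and 1/5 splits, analysing all 39 as assigned with every week-6 value observed gave 4.9% to 5.0% and a mean difference of 0.000 to 0.002 SD.

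**The case against.** The strongest reply has four parts.

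**The mechanisms are possibilities.** The stopping rule in Section 12 and the freedom to withdraw in Section 14 apply to both arms. Section 12 does not say that a participant who stops leaves the analysis, or whether stopping is for one session or for good. Online adherence is not unobserved, since weekly meetings and posted records cover it. This stands. A reader might infer that the online arm lost more people, that participants with worse pain were removed, or that the rule was picked after the results were seen. The documents support none of these.

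**The bias may be small.** It stays within about 0.32 SD even when all six exclusions fall in one arm with a 1 SD gap, against a standard error of about 0.35 SD. A 4-to-2 split barely moves the false-positive rate. This also stands, and it is why the point is not rated as a must-fix.

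**As-assigned analysis may change nothing.** If the six are dropouts with no week-6 values, an analysis of available values uses the same people, and the 5% comparator cannot be reached. This stands for a completed trial. VAS, NDI and HADS are measured only at baseline and week 6, so little else is available to inform their missing values. A shift analysis shows how far the result depends on those values but does not recover them.

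**The flow diagram may report exclusions.** It may, so the request for that report is conditional. It does not remove the need for a defined set and an as-assigned analysis in Section 13.

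**Conclusion.** The point holds as a should-fix. It is certain that per-protocol is the only set named and that the visible text neither defines it nor adds an as-assigned analysis. With no margin stated and a two-tailed difference test, the design offers no reason to rely on per-protocol alone.

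The sign and size of any bias are unknown. The range of about -0.32 to +0.30 SD, with false-positive rates from 5% to about 14%, rests wholly on the assumed arm sizes, six exclusions and a gap of 0.5 to 1.0 SD. Its ends need every exclusion in one arm. There is no bias if nobody was excluded or if exclusion is unrelated to outcome. Concluding that the trial's result is biased, or biased toward online delivery, would go beyond the documents. Confidence is high for the omission and low for a material effect on the result.

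**What to change.** 1. In Section 13, make the primary analysis all randomised participants in their assigned group, whatever their adherence, using every available week-6 value.
2. If the trial is still running, collect week-6 outcomes from those who stop exercising.
3. Keep per-protocol as a secondary analysis, with one written rule applied alike in both arms.
4. Report exclusions by arm and reason, if the flow diagram does not already do so.
5. Add a sensitivity analysis that shifts missing week-6 values, for example by 0 to 1 SD in either direction and separately by arm.

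**Cost.** In a running trial: revised wording, a few extra questionnaires and a little more analysis. In a completed trial, which the largely past-tense text suggests: a re-analysis. That changes the estimate only if participants with week-6 data were excluded; otherwise the gain is the sensitivity analysis. The downside is that non-adherence may slightly dilute the as-assigned estimate.

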#### **Study Design**

The present study was an assessor blinded randomized controlled trial conducted according to the Declaration of Helsinki (World Medical Association, 2013). The Institutional Review Board of the Beijing Sport University approved the study (reference number: 2023006H).

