#### **Study Duration**

Totally 8 weeks, including 1-week baseline testing, 6-week intervention and 1-week post intervention testing.

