## 7. Objectives:

People with chronic neck pain suffer from persistent pain with impaired physical function and mental health. The proportion of mental issues among them is much higher than healthy population. The purposes of this study were to compare the efficacy of online exercise therapy with conventional exercise therapy on pain, function, psychological status and work efficiency of young adults with chronic neck pain.

Objective outcome assessments were taken at baseline prior to randomization and after the 6-week intervention period. Additional assessments of the Work Limitations Questionnaire were done after two weeks and four weeks of intervention.

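### Per-protocol, left undefined, is the only analysis population for the online-versus-conventional comparison of VAS and NDI change

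*Combined protocol and SAP*

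**What the plan says.** Section 5 (Study Design) describes the trial in these words: "The present study was an assessor blinded randomized controlled trial". The primary outcomes are average VAS, maximum VAS and NDI. Section 13 compares change scores between arms with a two-tailed independent-sample t test and fixes the population with "Per-protocol analysis was used". It gives no minimum number of sessions, no list of deviations and no rule for people who stop early. The readable text plans no analysis by assigned arm, no sensitivity analysis and no method for missing scores.

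The final assessment is not conditional on adherence. Section 5 (Study Duration) has "Totally 8 weeks, including 1-week baseline testing, 6-week intervention and 1-week post intervention testing", and section 7 has "Objective outcome assessments were taken at baseline prior to randomization and after the 6-week intervention period".

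Adherence is seen differently in the two arms. Under section 10, control participants attend every session in small laboratory groups. The online arm has one group video session a week, and for the rest: "Then the participants performed the remaining two sessions of exercises themselves weekly". Section 8 describes online delivery as "with videoconferencing once a week and posting of exercise record on WeChat app twice a week".

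On leaving the study, section 14 says only "Participants can drop out at any time during this study". It does not separate stopping the exercises from leaving follow-up.

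**The concern.** Randomisation makes the arms comparable as allocated. A per-protocol rule selects on what happens afterwards, and that can be related to pain and function. Because the rule is not written down, three things are left open: whether a participant with a week-6 score can be excluded for missed sessions, how many missed sessions would count, and when this is decided. Nothing prevents the decision being taken once the scores are known.

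The difference in how adherence is observed adds to this. Attendance in the laboratory is witnessed. Two of every three online sessions are done alone and known through posted records. The same nominal rule could therefore remove different kinds of people from each arm. What is at stake is the VAS and NDI difference between delivery modes, with no as-randomised result planned to set beside it.

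**Working it through.** **The plan's own figures.** The plan attaches no number to the analysis population. The nearest figure is the sample size: 32/(1 − 0.15) = 37.6, rounded up to 38, against 39 stated. The 32 itself matches a one-tailed test at 0.9 SD (16 per arm); the two-tailed test stated needs 21 per arm, or 42. That is a separate matter, and nothing below depends on it.

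**Can someone with a score be excluded?** Sections 5 and 7 schedule the post-intervention assessment for participants without an adherence condition, so a person who missed sessions can have a week-6 score. Section 13 then restricts the analysis to an undefined per-protocol group. Taken together, the text permits exclusion of a scored participant. It does not require it.

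**Does the design call for per-protocol?** In an equivalence or non-inferiority trial, per-protocol is often given weight beside the as-randomised analysis. Here the test is for a two-tailed difference and no margin is stated, so that argument is not available.

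**Illustration of size.** Inputs:
- Total of 39 (section 13). The split of 20 and 19 is assumed, because no allocation ratio is stated.
- k1 and k0: scored participants excluded from the arms of 20 and 19 (assumed).
- d: how much worse, in SD, an excluded participant's change is than that of those retained (assumed 0 to 2, the same in both arms).
- Planned effect 0.9 SD (section 13), for scale.

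Leaving out k of n participants raises that arm's mean improvement by (k/n) × d, so the shift in the group difference is |k1/20 − k0/19| × d.

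| Exclusions | Multiplier | d = 0 | d = 0.5 | d = 2 |
|---|---|---|---|---|
| One, from the arm of 20 | 1/20 = 0.050 | 0 | 0.025 | 0.100 |
| One, from the arm of 19 | 1/19 = 0.053 | 0 | 0.026 | 0.105 |
| Two, from the arm of 20 | 2/20 = 0.100 | 0 | 0.050 | 0.200 |
| Two, from the arm of 19 | 2/19 = 0.105 | 0 | 0.053 | 0.211 |
| One from each arm | 0.053 − 0.050 = 0.003 | 0 | 0.001 | 0.005 |

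For one exclusion the largest shift is 0.105/0.9 = 11.7% of the planned effect. The standard error of the difference with 38 analysed is sqrt(1/19 + 1/19) = 0.324 or sqrt(1/20 + 1/18) = 0.325 SD, so the same shift is 0.105/0.325 = 32% of one standard error.

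If the excluded person had done better than the rest, for example by stopping once the pain had gone, d changes sign and so does the shift.

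**The case against.** The strongest reply is that per-protocol may mean no more than leaving out dropouts who have no week-6 score. In section 13 the term sits close to a 15% dropout allowance, which fits that reading. An analysis of everyone with a week-6 score would then include the same people and change nothing. This stands as an open possibility. It does not remove the point, because the text does not choose between the two readings.

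A reader might go further and infer that people whose neck pain flares are taken out of the pain comparison, since section 12 says "if there are adverse reactions such as acute aggravation of neck pain, the test or intervention will be stopped immediately". The documents do not support that. The sentence covers stopping a test as well as the intervention and leads straight to emergency treatment and basic life support, so it reads most naturally as first aid within a session. Nothing makes the stop permanent or ties it to the analysis, and section 15 calls the risk rare.

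A reader might also infer that stopping would differ between arms because supervision does. The documents show a difference in how adherence is observed, not in how many people stop.

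It is also fair to say that the illustrated effect is small and rests on assumed inputs. A larger shift needs several exclusions concentrated in one arm. Finally, the flow diagram in section 11 could not be read here. It may give discontinuations and numbers analysed by arm, so by-arm reporting cannot be called absent.

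**Conclusion.** The point holds as a design choice that should be changed. An undefined per-protocol group is the only population named for a randomised two-tailed difference test, and a better main analysis is available at almost no cost. That conclusion rests on the text of section 13 and needs no assumption about who stops or why.

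The bias itself is unknown in size and direction. Under the assumptions shown, it is 0 to about 0.11 SD for one excluded participant, 0 to about 0.21 SD for two in the same arm, and about 0 for one similar exclusion in each arm. It is tempting to say that those who stop exercising will probably be left out. That rests on the usual meaning of per-protocol, not on anything the plan says; the supportable statement is that the plan allows it.

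**What to change.** 1. In section 13, make the main analysis a comparison by assigned arm of everyone with a week-6 score, whatever exercise they completed, using the planned t test.
2. Keep per-protocol as a supportive analysis and define it before analysis, for example by a minimum number of the 3 × 6 = 18 sessions, with the same source of session counts described for each arm.
3. In sections 12 and 14, state that stopping exercise is not withdrawal from follow-up and that people who stop are still asked to attend the week-6 assessment already scheduled.
4. Report missing week-6 scores and their reasons by arm. This is needed because the analysis in item 1 still omits anyone without a week-6 score.

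The cost is one more run of the same t tests, some added wording, a protocol amendment (the ethics board has approved the study), and the questionnaires of any stoppers who would otherwise not have been asked. Their number cannot be fixed in advance, since 15% is an anticipated dropout rate and not a ceiling. The main downside is that including non-adherent participants may dilute a difference between arms, which is why the defined per-protocol analysis stays. Section 13 is written in the past tense; if the data are already collected, items 1 and 4 can still be done for everyone assessed.

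### The stated two-tailed inputs do not give 32: power is about 69% at 32 analysed and about 71% at the 33 expected completers, not 80%

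*Combined protocol and SAP*

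**What the plan says.** All the inputs except the allocation ratio stand in section 13 (Statistical Analysis Plan) of the combined protocol and SAP.

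- Result: "The sample size for the study was calculated to be 32", using G*Power.
- Effect size: "an estimated effect size of group difference of 0.9 in primary outcomes".
- Alpha: "a level of significance of 0.05".
- Power and test: "statistical power of 80% with two-tailed independent sample t test".
- Sidedness of the analysis: "The level of significance of all statistical tests was set with two-tailed at 0.05".
- Analysis set: "Per-protocol analysis was used".
- Enrolment: "With an anticipated dropout rate of 15%, a total of 39 participants was required".

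The planned between-group analysis is an unadjusted independent-samples t test on change scores, so the sample-size test and the analysis test agree. On allocation, section 8 says only "They were randomly assigned into two groups". No ratio appears in the text available. The flow diagram in section 11 is not reproduced there.

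**The concern.** For a standardised difference of 0.9, a two-tailed t test at 0.05 with 16 per arm looks too small for 80% power. If so, the only sample-size justification in the document claims a property the design does not have.

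This matters for how a non-significant result is read. The two arms receive the same exercise programme by different modes of delivery, so a finding of no difference is plausible. Readers will weigh it against the stated 80%, and an overstated figure makes such a result look more informative than it is. Because the analysis is per protocol, the number that counts is the number who complete, not the number enrolled.

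**Working it through.** **Inputs.** From section 13: d = 0.9, alpha = 0.05, target power 80%, independent-samples t test, 32 analysable, 39 enrolled, 15% dropout. Assumed: 1:1 allocation. For a fixed total this gives the highest power, so the assumption favours the plan.

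**Formula.** Exact power from the noncentral t distribution, with df = n1 + n2 − 2 and noncentrality λ = d × √(n1·n2/(n1 + n2)). Two-tailed power is P(T > t*) + P(T < −t*), where T is noncentral t with parameters df and λ, and t* is the 0.975 quantile of the central t. One-tailed power is P(T > t*) with the 0.95 quantile.

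**Step 1: try to reproduce 32.** At 16+16, λ = 0.9 × √(256/32) = 0.9 × 2.828 = 2.546, with df = 30.

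- Two-tailed, t* = 2.042: power 69.3%. The stated 80% is not reproduced.
- One-tailed, t* = 1.697: power 80.03%. At 16+15 it is 78.8%, so 32 is the smallest total that reaches 80% in a one-tailed test.

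**Step 2: power of the plan as written.** Expected completers: 39 × 0.85 = 33.15, so about 33.

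| Analysed | λ | Two-tailed t* | Two-tailed power |
|---|---|---|---|
| 16+16 (the stated 32) | 2.546 | 2.042 | 69.3% |
| 17+16 (15% dropout from 39) | 2.584 | 2.040 | 70.7% |
| 20+19 (no dropout) | 2.809 | 2.026 | 78.1% |
| 20+20 | 2.846 | 2.024 | 79.2% |
| 21+20 | 2.881 | 2.023 | 80.2% |
| 21+21 | 2.916 | 2.021 | 81.2% |

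At 17+16 the shortfall is 80 − 70.7 = 9.3 percentage points, and the type II error is 100 − 70.7 = 29.3%. The difference detectable with 80% power is 1.02 SD at 16+16 and 1.01 SD at 17+16.

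**Step 3: size that does meet 80%.** With equal arms, 42 analysable. Enrolment: 42/0.85 = 49.4, so 50. If the arms may differ by one, 41 suffice: 41/0.85 = 48.2, so 49.

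**Step 4: other explanations for 32.**

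- *Rounding of the effect size.* d = 0.949, about the largest value that rounds to 0.9, gives 73.8% at 16+16 and 75.2% at 17+16. At d = 0.95, 38 analysable are still needed.
- *Normal approximation instead of exact t.* This gives 40, not 32.
- *Unequal allocation.* Power falls: 65.6% at 22+11 and 73.3% at 26+13.
- *32 per arm rather than in total.* Power would be 94.3%, and 39 enrolled could not supply it.
- *Covariate adjustment.* An ANCOVA with a baseline correlation of about 0.5 would need 32, but section 13 names an unadjusted t test for both the sample size and the analysis.

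**Step 5: the dropout step.** 32/0.85 = 37.6, so 38. The stated 39 is one higher and is not part of the error.

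**The case against.** The arithmetic at 32 is not open to dispute. The better objections concern how firmly the rest can be stated.

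- *The allocation ratio may be in the flow diagram, which cannot be seen.* That is fair, and the point should be read as 'not stated in the text available'. It does not rescue 32, because 1:1 is already the best case.
- *The 33 completers are an assumption.* Section 13 does not define the per-protocol set, and non-adherence could remove more people than dropout does, particularly as two of the three weekly online-arm sessions are done without supervision. So 70.7% holds if dropout is the only loss and is balanced across arms. The figure that needs no such assumption is 69.3% at the stated 32.
- *Power is per outcome.* The synopsis counts three primary outcomes, and 0.9 is applied to them collectively. The figures here are for one outcome at an unadjusted 0.05. A multiplicity adjustment would lower them, so the restated sentence should say 'per outcome'.
- *The one-tailed explanation is inference.* It is. The match is exact, but the error does not depend on it.
- *The section is in the past tense, so a correction may change no design decision, estimate or p-value.* This is the strongest argument for treating the matter as less urgent, and type I error is indeed unaffected. But the public plan makes a claim its own inputs contradict, and that claim bears directly on how a null result is read.

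**Conclusion.** The concern holds. Under the inputs in section 13, 32 analysable participants give 69.3% two-tailed power, not 80%. The 33 expected from 39 enrolled give 70.7%, about 9 percentage points short, and even complete retention of 39 gives only 78.1%. With equal arms, 42 analysable are needed.

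This rests on d = 0.9 as stated, 1:1 allocation and a single outcome tested at an unadjusted 0.05. The 70.7% also assumes dropout is the only and a balanced loss. Departures such as unequal arms, further per-protocol exclusions or a multiplicity adjustment would all lower the power. A one-tailed calculation is the likely source of 32, but this is unconfirmed. If it is the source, the sample-size sentence misdescribes its own calculation and still needs correcting. This must be fixed, because it is the document's only sample-size justification.

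**What to change.** Change section 13 only. Suggested wording:

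> With 39 enrolled and 15% dropout, about 33 participants are expected to be analysable. With 1:1 allocation, a two-tailed independent-samples t test at alpha 0.05 has about 71% power for d = 0.9, per outcome and without multiplicity adjustment (about 69% with 32 analysable). 80% power would need 42 analysable participants with equal arms, or about 50 enrolled with 15% dropout.

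Give the actual allocation ratio in the same passage, and recompute the figures if it is not 1:1. Because the section is written in the past tense, record this as a dated correction that leaves the 32 and the 80% visible. The 42 and 50 are there for information. Enrolment stays at 39, and the test and alpha do not change.

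The cost is a few sentences and a less favourable stated power.
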